6.2.2 Study endpoints

The primary endpoint for this study is the plasma concentration of AZD6140 and the metabolite AR-C126910XX when released from the Enterion capsule in the proximal and distal small bowel and the ascending colon.

PK parameters derived from the Enterion limbs of the study, as well as plasma concentrations of AZD6140 and the metabolite AR-C126910XX when given as an IR tablet and an oral suspension are considered to be secondary endpoints.

6.2.3 Statistical analyses

All pre-treatment group characteristics will be summarised and presented using standard summary statistics. No statistical hypothesis tests will be carried out on baseline data.

No formal statistical tests will be done on any pharmacokinetic data. The plasma concentration data will be summarised, by timepoint. PK parameters will be calculated for each subject, and summarised by treatment limb. Individual and mean plasma concentrations and pharmacokinetic parameters will be summarised and presented in tabular format and/or graphically. Descriptive statistics will be applied to the data.

Adverse Events

Adverse events will be summarised by System Organ Class and Astra Preferred Term, using Astra Adverse Event Terminology. All adverse events will be noted as being emergent during pre-treatment (prior to any study drug being given to the subject), or treatment-emergent (if they appear following administration of study drug). If an adverse event is treatment-emergent, it will be assumed to be emergent due to the last dose level having been administered to that subject.

All adverse event data will be listed for all subjects. Separate listings of all serious adverse events, deaths or other significant adverse events, as assessed by the study responsible physician, will be presented.

Adverse event data will be summarised by causality (whether there is a reasonable possibility that the event is causally related to study drug 'Yes' or 'No') and intensity, and by causality and seriousness, by treatment emergence category. Summaries will be presented by treatment limb.

Laboratory data

All laboratory safety data, incorporating haematology, clinical chemistry and urinalysis data, will be listed, with deviations from the normal ranges explicitly noted on the listings.

Numerical laboratory safety data will be summarised using standard summary statistics by scheduled timepoint. Raw values will be summarised for the Visit 1, pre-dose baseline measurements and follow-up measurements, and within-subject changes from baseline for the post-treatment measurements. Summaries will be presented by treatment limb.

Discrete laboratory safety data will be summarised showing the number of subjects at each level of measurement at each scheduled timepoint. These summaries will be presented by treatment limb.

Figures comparing the post-treatment measurements against the pre-treatment measurement will be produced for each numerical laboratory safety measurement. These figures will be presented by treatment limb.

Vital signs data

Vital signs data will be summarised using standard summary statistics by scheduled timepoint. Summaries will present raw values for each visit including pre-dose baseline measurements, and within-subject changes from baseline for all other measurements. These summaries will be presented by treatment limb.

Vital signs measurements will be presented as mean plots across time, presented by treatment limb.

ECG data

ECG data will be summarised using standard summary statistics by scheduled timepoint. Numerical summaries will present summaries of raw values for each visit, including pre-dose baseline measurements, and within-subject changes from baseline for all other measurements. These summaries will be presented by treatment limb.

ECG intervals will be presented as mean plots across time, presented by treatment limb.

Physical examination data

Abnormal physical examinations will be listed and summarised by treatment limb. For the summaries, the number of abnormalities within each examination category will be used for Visit 1, and data at Visit 7 will be categorised as either normal; abnormal but unchanged from Visit 1; and newly abnormal.

Other safety data

All other safety data will be listed and summarised using suitable summary statistics, where appropriate.

All subjects allocated to treatment will be included in the analysis set and all data will be assigned to the treatment received. Exclusions from this analysis set will be documented in the statistical analysis plan prior to clean file; examples include, but are not limited to, major deviations in the administration of study compound or co-administration of medications expected to affect the data.

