There will be 5 treatment limbs. On each limb subjects will receive a single dose of study treatment. The first 2 study periods will last approximately 24 hours. The third, fourth and fifth study periods will last approximately 28, 31 or 48 hours, depending on the treatment allocation. Subjects will be required to return to the clinical unit at 36 hours either post-dose or post-activation for all regimens. Each capsule administration will be separated by a washout period of no less than 96 hours.

Endpoints

- Pharmacodynamic

Scintigraphic imaging – Gastric emptying time, small intestinal transit time, ileo-caecal junction (ICJ) arrival time, residence time at ICJ, colon arrival time, colon transit time, total transit time, time and anatomical location on successful Enterion activation.

- Safety

Haematology, clinical chemistry, urinalysis, blood pressure, pulse, 12-lead ECG and adverse events.

- Pharmacokinetic

The plasma concentration data for AZD6140 and the metabolite AR-C126910XX will be analysed using standard pharmacokinetic methods to yield the following parameters:

AUC, AUC_t, t_{1/2}, C_{max}, t_{max}.

Individual and mean plasma concentrations and pharmacokinetic parameters will be summarised and presented in tabular format and/or graphically by AstraZeneca R&D Charnwood. Descriptive statistics will be applied to the data.

Statistical methods

All data will be summarised using suitable summary statistics, where appropriate. No formal statistical analysis will be performed on any of the data.

	PAGE
PROTOCOL SYNOPSIS.....	2
LIST OF ABBREVIATIONS AND DEFINITION OF TERMS	9
1. INTRODUCTION.....	11
1.1 Background	11
1.2 Rationale for this study.....	12
2. STUDY OBJECTIVES	12
2.1 Primary objective	12
2.2 Secondary objectives.....	12
3. STUDY PLAN AND PROCEDURES.....	12
3.1 Overall study design and flow chart.....	12
3.2 Rationale for study design, doses and control groups.....	15
3.3 Selection of study population	15
3.3.1 Study selection record	15
3.3.2 Inclusion criteria.....	16
3.3.3 Exclusion criteria.....	16
3.3.4 Discontinuation of subjects from treatment or assessment	18
3.3.4.1 Criteria for discontinuation	18
3.3.4.2 Voluntary discontinuation by a subject.....	18
3.3.4.3 Incorrectly enrolled or randomised subjects	18
3.3.4.4 Procedures for discontinuation.....	19
3.3.5 Restrictions.....	19
3.3.5.1 Dietary restrictions	19
3.3.5.2 Activity restrictions	19
3.4 Treatments.....	20
3.4.1 Investigational products	20

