Investigational Products (IPs), AstraZeneca R&D Charnwood will provide a Subject/Treatment allocation sheet, providing the treatment sequence for each subject. During the course of the study it may be necessary to revise the allocation of the treatments administered at Visits 4, 5 and 6, for individual subjects, for example, to accommodate rapid gastrointestinal transit. In the event of a missed activation where the treatment cannot be reallocated, the capsule will not be activated. In this instance a subject may be asked to return to the clinical unit for an additional study day providing the amount of blood that will be taken from the subject over the study is still within the range accepted by the Ethics Committee and that the radiation dose will not exceed the yearly limit. Furthermore, should retrospective analysis indicate that the capsule has been activated in the incorrect site, the subject may be asked to return for an additional study day. Additional study days will be approved by the Principal Medical Investigator and AstraZeneca R&D Charnwood and the Ethics Committee.

Each dosing occasion will be separated by a washout of no less than 96 hours.

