4.4 Safety measurements and endpoints

4.4.1 Summary of safety objectives and endpoints

Table 3 shows how the safety endpoints of this study relate to the study objectives.

Table 3 Safety objectives and endpoints relating to each objective

Objective	Endpoints	Summary statistic for analysis (including timepoint and population)	Planned analysis	Significance of results
To assess the safety and tolerability of 100 mg AZD6140 when given as an IR tablet, an oral suspension and suspension/powder delivered to 3 different sites in the GI tract	Haematology, clinical chemistry urinalysis, ECG and BP & Pulse.	Change from baseline (pre-dose at each visit)	Summary statistics (mean, SD, min, max)	Clinical review of all values outside the reference ranges
	Incidence, nature and severity of Adverse Events	Incidence rate summarised by treatment limb	Summary of AEs during each study period	Individual subject safety monitoring

The methods for collecting safety data are described below.

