4.4.4 Other safety measurements and variables

4.4.4.1 Methods of assessment

Vital signs

Supine and standing blood pressure (mmHg) and pulse (bpm) will be measured. Supine blood pressure will be measured after 5 minutes in the supine position. Standing blood pressure will be measured after 2 minutes standing.

Supine and standing blood pressure and pulse measurements will be taken at the following timepoints:

Visit 1 (enrolment).

Visits 2 and 3: pre-dose, 1, 2, 4, 12 and 24 hours post-dose.

Visits 4, 5 and 6: pre-dose, pre-activation, 1 (standing only), 2 (standing only), 4 (standing only), 12 (standing only) and 24 hours post-activation.

Visit 7 (follow-up).

Blood pressure and pulse will be recorded using a semi-automatic blood pressure recording device (Omron) with an appropriate cuff size.

12-lead ECG

A 12-lead ECG and rhythm strip will be recorded at the following timepoints:

Visit 1 (enrolment).

Visits 2 and 3: pre-dose, 1, 2, 4, 12 and 24 hours post-dose.

Visits 4, 5 and 6: pre-dose, pre-activation, 1, 2, 4, 12 and 24 hours post-activation.

Visit 7 (follow-up).

The ECG will be performed using an automated machine (Schiller) which is programmed to provide an electronic interpretation of the electrocardiogram. These reports may be qualified by the investigator since the programme cautiously overstates potential abnormalities. A medically qualified person will assess the ECG parameters, and make an overall evaluation. Data obtained from the ECG traces (PR, QRS, QT, QTc interval, sinus rhythm, overall evaluation and any comments) will be directly entered into the study database by Data Management personnel, AstraZeneca R&D Charnwood.

Physical examination

Physical examinations will be performed at enrolment (Visit 1) and at the post-study follow-up visit (Visit 7). A medically qualified person will perform this examination.

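### In the Enterion limbs, adverse events and ECG or blood-pressure shifts that occur before drug release are credited to a release site

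*Protocol*

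**What the plan says.** **Adverse events (AEs).** Section 6.2.3 has two emergence classes. An event is pre-treatment if it arises "prior to any study drug being given to the subject", and "treatment-emergent (if they appear following administration of study drug"). For a treatment-emergent event, "it will be assumed to be emergent due to the last dose level having been administered to that subject". Summaries are then given by treatment limb.

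**Baseline.** Table 3 (Section 4.4.1) sets the summary for laboratory tests, ECG, blood pressure and pulse as "Change from baseline (pre-dose at each visit"). Section 6.2.3 treats every other ECG and vital-sign reading as a change from that value. Yet Section 4.4.4.1 schedules ECGs at "Visits 4, 5 and 6: pre-dose, pre-activation, 1, 2, 4, 12 and 24 hours post-activation", and blood pressure and pulse are also read just before activation.

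**Swallowing and release.** The synopsis says "Each capsule administration will be separated by a washout period of no less than 96 hours". Section 3.4.2 has the capsule doses taken at about 11:00, with activation following at a time that varies between subjects. Appendix G puts 0 hours at swallowing and lists activation as a later step. The synopsis also says: "The third, fourth and fifth study periods will last approximately 28, 31 or 48 hours, depending on the treatment allocation". Section 3.4.2 adds: "In the event of a missed activation where the treatment cannot be reallocated, the capsule will not be activated".

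**The concern.** In the tablet and oral suspension limbs, administration and exposure begin together. In the capsule limbs they do not: the subject has swallowed a sealed device and a tracer drink, and none of that limb's drug is available until activation. Section 6.2.3 has no category for this interval, because its only pre-treatment class closes at the first dose of the whole study (Visit 2). An event in the interval is attributed to a site that the drug has not reached.

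The same gap affects ECG and vital signs. Each post-activation change from the pre-dose value includes whatever happened between swallowing and release. In a long wait that can include lunch, dinner and a night of interrupted imaging.

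The wording adds a smaller problem. All five limbs are 100 mg, so the term dose level does not identify a limb.

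Table 3's safety objective concerns drug delivered to three gut sites, and AE incidence by limb is its stated summary. With 10 to 12 subjects, one subject wrongly counted moves a limb's incidence by 1/12 = 8 to 1/10 = 10 percentage points.

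**Working it through.** The protocol states no figure for the pre-release interval, so there is none to reproduce. It can be derived.

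**Inputs**
- Capsule period lengths: 28, 31 and 48 h (synopsis). Matching them in that order to proximal, distal and colon is an inference from the order of transit.
- Discharge: 24 h after activation (Sections 3.3.5.2 and 4.3.1.1).
- Admission about 07:00, capsule dose about 11:00, so 4 h apart (Section 3.4.2).
- Minimum interval between doses: 96 h (synopsis and Section 3.4.2).

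**Time from swallowing to release** = period length − 24 h, less a further 4 h if the period runs from admission.

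| Limb (inferred) | Period from swallowing | Period from admission |
|---|---|---|
| Proximal | 28 − 24 = 4 h | 4 − 4 = 0 h |
| Distal | 31 − 24 = 7 h | 7 − 4 = 3 h |
| Colon | 48 − 24 = 24 h | 24 − 4 = 20 h |

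The first reading fits Visits 2 and 3 better, where the period is about 24 h and discharge is 24 h after dosing. The 0 h figure is only a lower bound, because proximal activation waits for gastric emptying (Section 4.3.1.1).

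**Share of the AE attribution window.** Section 6.2.3 attributes an event to the last dose administered, so a limb's window runs to the next dose. At the 96 h minimum:
- Proximal: 0/96 to 4/96 = 0-4%
- Distal: 3/96 to 7/96 = 3-7%
- Colon: 20/96 to 24/96 = 21-25%

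A longer interval between doses makes these shares smaller.

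**Number of events.** The documents give no background AE rate. Assuming 0.02 to 0.10 events per subject-day and 12 subjects, expected pre-release events = 12 × rate × hours/24. With 4, 7 and 24 h this gives:
- Proximal: 0.04 to 0.20
- Distal: 0.07 to 0.35
- Colon: 0.24 to 1.2

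**Can the data separate the two phases?** Activation time is recorded (Section 4.3.1.1), and ECG, blood pressure and pulse are taken just before activation. But Section 4.4.2.2 asks for the clock time of AE onset only where relevant, and schedules no AE question between admission and 1 h after activation. Without an onset time, an event on the day of activation may not be placeable before or after release.

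**The case against.** **The size is easily overstated.** A reader might infer that the colon limb would show about 50% more events, from windows of 24 + 36 = 60 h and 4 + 36 = 40 h. That requires attribution to stop 36 h after activation, and nothing in the protocol stops it there. AEs are collected throughout, and the rule carries an event to the last dose given. If 96 h separates swallows, the minimum window is the same for every site. This stands: a longer colon window, or a colon limb that looks worse, is not established.

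**Drift need not grow down the gut.** Release 20-24 h after an 11:00 dose falls between 07:00 and 11:00 next day, close to the clock time of the pre-dose reading. For time of day, the colon limb may be the best matched. This stands too.

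**Pre-dose is a defensible baseline.** It is defined alike in all five limbs, and the pre-activation value appears at its own timepoint, so a shift before release would be visible. That is true, but every post-activation change would still contain the shift.

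**Never-activated capsules have a route.** A reader might infer that they must collect events for their planned site. Section 6.2.3 assigns data to the treatment actually received and allows documented exclusions for major administration deviations. What is lacking is an explicit rule for this case.

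**Other mitigation.** Post-release assessments are already timed from activation. All AEs are listed, summaries are split by causality, and Appendix F asks whether the drug was actually received. Section 6.2.3 does not itself say that administration means swallowing; that comes from usage in the synopsis, Section 3.4.2 and Appendix G. Nor are the subjects drug-naive: they have had earlier doses, so the gap precedes release of that limb's dose, not all exposure.

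**Conclusion.** The point holds in a limited form. As written, the AE rule and the pre-dose baseline credit events and shifts before release to a release site, unequally between sites: about 21-25% of a minimum 96 h interval for colon against 0-4% for proximal. These figures rest on the inferred match of periods to sites, on periods starting at swallowing or at admission, and on the minimum interval. They measure time at risk of misattribution and are not a predicted excess of events.

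Severity is modest. The study is open and descriptive, safety is secondary, and the expected number of misattributed events is small. It is still worth correcting now. The baseline and AE rule are fixed in the protocol, so a SAP (not among the documents reviewed) would have to depart from them, and it could not recover onset times that were never recorded.

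**What to change.** Amend Section 6.2.3 and Table 3 for Visits 4-6:

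1. Report AEs with onset between swallowing and the recorded activation time in a separate category, such as capsule swallowed, drug not yet released. Count site-attributed AEs from activation. Do not move pre-release events to the previous limb: that would charge a possible capsule or procedure effect to a dose from an earlier visit.
2. Require the clock time of AE onset at these visits.
3. Use the pre-activation ECG, blood pressure and pulse (same posture) as baseline for post-activation changes, and still show the change from pre-dose to pre-activation.
4. State that a never-activated capsule contributes to no release site.
5. Replace dose level with treatment limb.

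The laboratory baseline stays pre-dose, because no pre-activation safety sample is taken.

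The cost is wording, one required CRF field and one extra AE category. There is also a trade-off: counting from activation within a fixed 96 h between swallows leaves 96 − 4 = 92, 96 − 7 = 89 and 96 − 24 = 72 h for proximal, distal and colon. Post-activation follow-up time should therefore be shown beside AE incidence for each site.

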3.4.4 Blinding and procedures for breaking the blind

As this is an open study, blinding is not required (see Section 3.2).

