3.4.5 Pre-study, concomitant and post-study treatment(s)

Subjects should abstain from taking medication (with the exception of paracetamol and HRT) which would interfere with the scientific conclusions of the study including over-the-counter preparations.

As a minimum, subjects should refrain from taking prescribed medications from 3 weeks prior to the first dosing occasion (Visit 2) until completion of the sample period at Visit 6 and OTC

preparations including herbal remedies and vitamin preparations from 7 days prior to the first dosing occasion (Visit 2) until completion of the sample period at Visit 6.

However, decisions about inclusion in the study should take into account the long half-life of some drugs and a longer period of exclusion may be necessary.

Aspirin is specifically prohibited from 3 weeks prior to Visit 2 until completion of the sample period at Visit 6 due to a potential increase in bleeding risk.

Other medication, which is considered necessary for the subject's safety and well being, may be given at the discretion of the investigator(s). The administration of all medication (including investigational products) must be recorded in the appropriate sections of the CRF.

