5. DATA MANAGEMENT

Data will be validated and quality checked by the AstraZeneca Monitor at the centre throughout the study. The original, edited CRFs will be returned to Data Management at AstraZeneca.

The data will be entered onto the AMOS database at AstraZeneca. The entered data will be manually checked against the originals and additional computerised checks will be run. Any missing, impossible or inconsistent entries in the CRF will be referred back to the investigator via the monitor within 3 working days of entering data using data query forms. Responses should be received and updated within 3 working days of generation.

Safety data comprising clinical chemistry, haematology and urinalysis will be reported by the department of Clinical Pathology at AstraZeneca R&D Charnwood and loaded into AMOS. Original paper printouts of the results will be sent to the study clinical investigator for comment and signature and then filed with the remainder of the CRFs.

Final quality control checks will be completed and error rates reported prior to a meeting to discuss the declaration of a clean data file. Protocol deviations detected during blind review of the data and during the data entry process will be considered for their effect on the analysis of the data. All decisions on the evaluability of data from each subject must have been made and documented in the Statistical Analysis Plan before declaration of clean file. The date of clean file will be documented within one day of the clean file meeting. The database will be locked and SAS® datasets will be extracted for the statistical analysis of the data.

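### The single analysis set in Section 6.2.3 lets PK-type exclusions remove dosed subjects from the safety summaries

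*Protocol*

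**What the plan says.** Section 6.2.3 goes in turn through baseline characteristics, PK data, adverse events, laboratory data, vital signs, ECG, physical examination and other safety data. It closes with one population for all of them: "All subjects allocated to treatment will be included in the analysis set and all data will be assigned to the treatment received". It continues: "Exclusions from this analysis set will be documented in the statistical analysis plan prior to clean file". The examples, which it says are not exhaustive, are "major deviations in the administration of study compound or co-administration of medications expected to affect the data". The protocol defines no separate safety or PK set.

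For adverse events, the same section says "All adverse event data will be listed for all subjects". The summaries name no population of their own. Table 3 in Section 4.4.1 plans adverse events as "Incidence rate summarised by treatment limb", and the laboratory, ECG, blood pressure and pulse data as change from the pre-dose value at each visit. Its column heading asks for the population, but no entry supplies one.

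Section 5 adds: "All decisions on the evaluability of data from each subject must have been made and documented in the Statistical Analysis Plan", to be completed before clean file. Section 3.4.5 prohibits aspirin because it might increase bleeding risk. It also allows the investigator to give other medicines needed for a subject's safety.

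**The concern.** A major dosing deviation or an interacting medicine is a sound reason to set aside a concentration profile, because the profile no longer describes absorption from the intended formulation or site. It is not a reason to set aside what happened to a person who took the drug. When one set serves both purposes, a decision made for PK reasons also removes that subject's safety data from the summaries.

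Such exclusions need not be unrelated to safety. A subject who takes aspirin alongside an antiplatelet agent is, on the protocol's own reasoning, at higher risk of bleeding, and is also a candidate for exclusion. A subject given a medicine to treat an adverse event could become excludable because of that event. The by-limb incidence would then tend to be too low, and a table and the listing beside it would rest on different subjects without the protocol saying so.

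At stake are the incidence and change-from-baseline summaries planned for secondary objective 2, safety and tolerability. The primary PK objective is not affected.

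**Working it through.** **Text check**

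1. *How many sets?* One. Section 6.2.3 speaks of the analysis set in the singular, and the exclusions are from that same set.
2. *Are the exclusions limited to PK?* No. The paragraph follows directly after the one on other safety data, and no wording restricts it.
3. *Do the safety summaries have their own population?* No. Neither Section 6.2.3 nor Table 3 names one, so they fall to the single set.
4. *Do the listings follow the same rule?* Not for adverse events, which are listed for all subjects. An event can therefore stand in the listing and be absent from the by-limb table.
5. *Is an exclusion by subject or by limb?* The text does not say. Section 5 refers to data from each subject. In a five-limb crossover, an exclusion by subject would remove all five limbs for a problem in one.

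**Size of the effect**

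The protocol states no figure on this point and made no formal sample size calculation, so there is nothing to reproduce. The following is illustrative.

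Input from the protocol: at most 12 subjects dosed (Section 3.1). Assumed: the number of events, the number of exclusions, and who had the event.

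Exact (Clopper-Pearson) 95% limits for x events in n subjects: the lower limit L solves P(X ≥ x | n, L) = 0.025, and the upper limit U solves P(X ≤ x | n, U) = 0.025.

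- All 12 kept, one event: 1/12 = 8.3%. L = 1 − 0.975^(1/12) = 0.2%. U solves (1 − U)^12 + 12U(1 − U)^11 = 0.025, giving 38.5%.
- That subject excluded: 0/11 = 0%. U = 1 − 0.025^(1/11) = 28.5%.
- A subject without the event excluded instead: 1/11 = 9.1% (0.2 to 41.3%). The incidence falls only when the excluded subject is one who had the event.

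The second illustration is the chance that a limb's summary shows at least one event when one of 12 subjects is excludable. Let p be the risk in the other 11 and q the risk in that subject. The chance is 1 − (1 − p)^11 (1 − q) if the subject is kept, and 1 − (1 − p)^11 if excluded. Take p = 5%, an assumption:

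| q (assumed) | Kept | Excluded |
|---|---|---|
| 5% (no extra risk) | 46.0% | 43.1% |
| 20% | 54.5% | 43.1% |
| 50% | 71.6% | 43.1% |

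The loss is small if the excluded subject is like the others, and grows with that subject's risk.

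**The case against.** The strongest reply is that Section 6.2.3 orders no exclusion from any safety summary. It leaves individual exclusions to the SAP, which is not shown and may define a safety set. Its wording about medicines expected to affect the data, and Section 5's about evaluability of data, can be read as decisions on particular data and not on whole subjects. This stands in part: the SAP could repair the matter. But the protocol itself fixes the single set and the grounds for leaving it. An SAP that follows the protocol inherits the problem, and one that adds a safety set departs from it.

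The second reply is that safety does not depend on the summaries alone. Table 3 also relies on clinical review of out-of-range values and on individual monitoring. Adverse events are listed for all subjects, serious and other significant events have separate listings, and all laboratory data are listed with deviations marked. This stands. A reader might infer that events could vanish from the report, but the documents do not support that.

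The third reply is that the route from treating an event to being excluded needs several steps: the medicine must be expected to affect the data, and someone must judge that a reason to exclude. Paracetamol and hormone replacement therapy are exceptions in Section 3.4.5. This is fair. The route is possible, and its likelihood is unknown.

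Three stronger readings are tempting but not supported:

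- *That capsule release at an unintended site is an excludable deviation with higher risk.* Sections 3.2 and 3.4.2 provide for reallocating limbs and for extra study days. Section 4.3.1.1 accepts transverse-colon release as complete data for up to two subjects, and data go to the treatment received. Every limb is a single 100 mg dose, and nothing shows more risk at another site.
- *That undosed subjects dilute the denominators.* The set does start from allocation, but subject numbers are given at Visit 2, the first dosing visit, after eligibility is established. Data are assigned to the treatment received, so an undosed subject should add nothing to a limb.
- *That 10 marks how far exclusions could go.* That figure is the minimum number of completers. It says nothing about exclusions.

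**Conclusion.** The point holds for the summaries. Section 6.2.3 applies one set, with open-ended exclusions of a PK type, to PK and safety alike. Followed as written, it can remove a dosed subject from the by-limb safety tables while the adverse event listing keeps that subject. The case is clearest for co-medication, where the protocol itself supplies the link to risk. For dosing deviations the link is weak, since Section 9.3 calls overdose unlikely.

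With at most 12 subjects dosed, one exclusion can move a limb's incidence from 8.3% to 0%. That assumes a single event, in the excluded subject. The two intervals overlap widely, and the study is descriptive, so no formal conclusion would change. What changes is whether a by-limb table shows an event at all. This merits correction because the rule is stated and the remedy is simple. It does not threaten the primary objective.

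**What to change.** In Section 6.2.3, replace the single set with two:

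- **Safety set:** every subject who received at least one dose, summarised by treatment received, with no exclusions for dosing deviations or co-medication. Use it for all adverse event, laboratory, ECG and vital-sign summaries, and name it in the population column of Table 3.
- **PK set:** the limbs of those subjects that give an evaluable profile. Apply the present exclusions here only, limb by limb, with each one documented before clean file as already planned.

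The SAP should carry the same definitions. The cost is a few sentences: no new data are needed, and the PK analysis keeps its present grounds for exclusion. The one downside for the sponsor is a possibly slightly less favourable safety table.
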